### 3. Study Procedures

- a) **N** Is this project a multicenter study (i.e., same project is conducted elsewhere by a different investigator) OR does this study involve conduct of research at multiple sites? Is SLU acting as a coordinating center for other sites OR is the SLU PI a direct recipient of a federal grant for this research? If yes, complete and attach the Supplemental Application for Coordinating Center Activities.

Will the SLU site be participating in all parts/procedures/arms of the study?

**If No, explain what SLU will NOT participate in:**

**Please save frequently**

Page numbers from a sponsor's protocol/grant may be referenced in 3b, 3c, and 3d.

- b) **Describe all the procedures, from screening through end-of-study, that the human subject must undergo in the research project, including study visits, drug treatments, randomization and the procedures that are part of standard of care. Specify which procedures are for research and which are standard of care. Please note: The box below is for text only. If you would like to add tables, charts, etc., attach those files in the Attachment section (#16).**

a.) Patients will have (standard of care) Endoscopic Sinus Surgery.  
 b.) Each patient will receive a hemostatic agent in one nostril and nothing in the other nostril.  
 c.) Products will be placed in patients' post-operative sinus cavities at the end of the procedure according to company recommended instructions. Essentially all products placed in the middle meatus are allowed to remain there until absorbed or removed at a post operative visit on weeks 1, 2, and 6. Post-operative irrigations (Standard of Care) will remove much of the material. Any residual material is removed in the office on normal, (Standard of Care) post-operative debridement on weeks 1, 2, and/or 6.  
 d.) Subjects will provide subjective pre- and post-operative data, such as rating their pain, bleeding, obstruction, and discharge on days 0, 1, 2, 7, and 14 (Standard of Care).  
 e.) Patients will be given a questionnaire packet pre-operatively (Research Related). Questionnaires will include post-operative data on days 0, 1, 2, 7, and 14. They are asked to bring completed questionnaires on standard post-operative visits.  
 f.) The physician will record objective and subjective data (synechiae, edema, infection, granulations, and time spent debriding) upon regular reexamination of the sinuses after surgery, at post-operative visits on weeks 1, 3, and 6. All procedures are standard clinical care.  
 g.) Follow up visits will conform to standard clinical care; patients will be seen in the physician's clinic.

**Protocol Title:** Analysis of hemostatic agents compared to physiologic hemostasis

---

clinic.

- c) If the proposed study is a clinical trial where a drug, vaccine, device or other treatment is compared to a placebo group or comparison treatment group, what are the guidelines or endpoints by which early decisions regarding efficacy or lack of efficacy can be made? For example, it may be reasonable to stop enrollment on a study when efficacy has already been clearly demonstrated, to avoid unnecessary enrollments of additional subjects. Alternatively, it may be reasonable to stop enrollment when it is clear that efficacy will never be demonstrated, given the statistical power of the study as designed. Describe the guidelines that are in place to assist in making these determinations, if relevant to the proposed study.

If side effects or discomforts do occur, [name] and/or [name] will try to minimize and treat these by irrigating the treated sinus with saline to remove the Arista, Nexfoam, Sinufoam, Nasopore, Posiseq, or Posiseq X.

- d) Describe how data analysis will be performed (statistical tests, methods of evaluating data) and indicate the smallest group/unit for which separate reporting will occur. For studies involving a questionnaire, if data and reliability information are available, please describe or provide references. For full board, unfunded studies describe sample size determination and power analysis. If none, please justify.

Means and standard deviations will be obtained for data collected from patients and the physician. These outcomes will be used for comparative evaluation of hemostatic agents (n=144) against no therapy. Statistics will include descriptive statistics and a non-parametric ANOVA comparing the questionnaire patient data and the physician data followed by Post-hoc multiple comparisons.

Please save frequently

- e) State if deception (including incomplete disclosure of study purpose/procedures) will be used. If so, describe the nature of the deception and provide a rationale for its use. Also, describe debriefing procedures or justify a waiver of the requirement to debrief. NOTE: for studies using deception, an alteration of consent must be justified in the Informed Consent section of the protocol (#13) and the debriefing script/statement must be uploaded in the Attachments section (#16). See IRB Deception Guidelines.

- f) Is there an accepted standard of care and/or standard practice at SLU for the condition/disease/situation being studied? This information will assist in comparing the risk/benefit ratio of study procedures relevant to usual care that would be received outside of the research context. **\*?HELP?\*** Y

If yes, please describe the standard of care and standard practice at SLU for the condition/disease/situation being studied.

There is no standard of care for the use of hemostatic agents - half of surgeons use an absorbable hemostatic agent and half use no hemostatic agent.

- g) Does this study involve any diagnostic imaging, labwork or genetic testing that could result in clinical discovery (diagnoses, genetic mutations, etc.)? Note that this could include discovery that is expected (related to the research) or incidental (not related to research aims, but possible, like a mass/shadow found in imaging despite not

**Protocol Title:** Analysis of hemostatic agents compared to physiologic hemostasis

---

looking for it).

If yes, please describe and include whether there are plans to share findings with study participants.

h) Is this study subject to the NIH Genomic Data Sharing Policy? N

The NIH GDS policy applies to all NIH-funded research that generates large-scale human genomic data as well as the use of these data for subsequent research and includes: genome-wide association studies (GWAS), single nucleotide polymorphisms (SNP) arrays, and genome sequence, transcriptomic, metagenomics, epigenomic and gene expression data, irrespective of NIH funding mechanism. Click here for more specific examples.

---

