**Please save frequently**

- c) Describe the study design (e.g., single/double blind, parallel, crossover, control, experimental, observational, etc.). If the study is investigator-initiated, a timeline for individual subject recruitment, follow-up, and analysis for the study is required. Also, indicate if the subjects will be randomized.

Our study is a prospective comparison between absorbable hemostatic agents as a group and the body's natural hemostatic ability without aid of therapy in patients undergoing bilateral sinus surgery with or without septoplasty.

We calculated the sample size and power analysis in the following way:

Given the number of statistical tests, we calculated a Bonferonni correction to set the alpha for the analysis at 0.017 (alpha originally at .05 divided by the number of tests = .05/30 = 0.017). Using G-Power statistical software, power analyses were completed using the Means: Wilcoxon-Mann-Whitney test (two groups). Given alpha at 0.017 and Power at 0.80, we determined that a total of 244 participants (122 in the control group, 122 in the hemostatics group) would be needed to detect a medium effect size (d=0.5). Since one nostril will be used as the control and the therapy applied to the other side, the number of participants needed drops to 122.

Based on previous studies, we conservatively expect a dropout rate of 15%. In order to maintain the same number of participants, we would need to enroll a total of 144 participants

Postoperatively, patients will rate subjective symptoms such as nasal obstruction, bleeding,

**Protocol Title:** Analysis of hemostatic agents compared to physiologic hemostasis

---

pain, and nasal discharge on a scale ranging from 1-10, of which 10 is the most severe. Similarly, the treating physicians on endoscopic examinations will rate objective measures such as mucosal edema, infection, time spent debriding, and synechiae formation. (Please see the attached patient and physician questionnaires) Patient questionnaires will be completed on postoperative days #1, 2, 7, and 14. Surgical healing outcomes will be noted during routine postoperative visits 1 and 2 weeks after surgery. Expected total duration of each subjects' participation is 6 weeks. Total subject accrual should take no longer than one year. Data analysis will take up to three months. Estimated time of completion is 03/2018.

d) **If subjects will be given placebo, please justify placebo use. \*?HELP?\***

N/A

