**Other (Please specify):**

3. If hardcopy materials are transported at any time in the study (e.g., from data collection site to storage site, shared with co-investigators), how are they secured?

Locked container

- X Personnel Supervision

Physical delivery (e.g., USPS, FedEx, Courier)

Fax Machine

SLU Email account with an encrypted file attachment

Non- SLU Email account with an encrypted file attachment

Other (Please specify):

4. Supplemental information related to above items can be entered here or leave blank:

- c) If a master list is used in this study (linking study codes to subject identifiers), explain: a) how and where you will secure the master list, b) how long it will be kept/when it will be destroyed, and c) provide a sample of the code.

a.) For initial data collection identifier information (name, MRN, etc.) will be necessary. The master list containing the identifier information of the subjects will only be available to the PI, co-investigator and study coordinator. This list will consist of a Study ID number and the identifiable information will be kept according to this ID. The list will be kept in a locked cabinet in the Department of Otolaryngology-- Head and Neck Surgery. Any data taken from the medical record will be manually entered onto data collection sheets identified by study number only. Medical Records will be obtained from Saint Louis University Hospital. This includes the sex, ethnicity, age, surgical pathology, treatment type and duration. In addition, pre-treatment and post-treatment radiographic imaging (CT scans and MRIs) is to be acquired from the Kodak™ Directview Radiology Image Server used at Saint Louis University Hospital respectively.

Since this is a prospective study, it is important to emphasize that the data and materials were obtained with the primary intention to diagnose and treat rather than for research purposes only. Existing records and data will continue to be used for treatment of future related sequelae of this disease process.

b.) The PI, co-investigator, and study coordinator will be the only people with access to identifiers or coded information.

c) No samples or data will be provided from an outside source.

d) We will not be audio/video taping or photographing subjects.

e) No data will be collected via email or the internet.

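### The supplied text does not state how the treated nostril is chosen, so the within-patient agent-versus-nothing comparison is open to side-selection bias

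*Combined protocol and SAP*

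**What the plan says.** Section 3b, item b: "Each patient will receive a hemostatic agent in one nostril and nothing in the other nostril". Section 2c uses the same structure to halve the sample size: "Since one nostril will be used as the control and the therapy applied to the other side". It describes the study as a "prospective comparison between absorbable hemostatic agents as a group" and the absence of therapy.

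The form asks about allocation twice. The prompt in 2c reads "Also, indicate if the subjects will be randomized", and the prompt in 3b lists what must be described, "including study visits, drug treatments, randomization and the procedures that are part of standard of care". Neither answer mentions randomisation, alternation, a fixed side or any other rule. Section 1a says only that one of the patient's nostrils is treated.

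On timing, 3b item c says "Products will be placed in patients' post-operative sinus cavities at the end of the procedure". On eligibility, 8h asks for a similar degree of sinus disease on the two sides. On analysis, 3d says "Statistics will include descriptive statistics and a non-parametric ANOVA comparing the questionnaire patient data and the physician data", followed by post-hoc comparisons; no term for side or for operative findings is stated.

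**The concern.** The main question is whether an agent is superior to no agent (1a), and 9.7 sets the goal of settling it definitively. The answer rests on the difference between two sides of the same nose. That difference estimates the effect of the agent only if the choice of side is unrelated to how the side would have done anyway.

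Whoever places the product can already see both cavities. The documents themselves link packing to bleeding: 10b says that non-absorbable packing is used when bleeding is excessive. Bleeding is also an outcome (2b, 2c). If the side were chosen on what is seen at the end of surgery, the side difference would mix the effect of the agent with the reason for the choice. Favouring the easier side would make agents look better than they are. Favouring the bloodier side would make them look worse and cost power. More patients would not average this out, and pooling the agents does not change it.

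**Working it through.** **The plan's own figures.** Section 2c gives Wilcoxon-Mann-Whitney, d = 0.5, power 0.80, 122 per group, then 122 patients, then 144 enrolled at 15% dropout.
- 0.05/30 = 0.00167. At one-sided 0.00167 the t-test needs 116.28 per group; multiplied by π/3 this is 121.8, so 122.
- 122/(1 − 0.15) = 143.5, so 144.
- The printed alpha of 0.017 would give about 75 (one-sided) or 89 (two-sided) per group. That is a separate matter. Neither 122 nor 144 depends on how the side is chosen.

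**What each stated safeguard covers.**

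| Feature | Where | What it controls | What it leaves open |
|---|---|---|---|
| Pairing within patient | 2c, 3b | Patient-level differences | Differences between the two sides |
| Similar bilateral disease | 8h | Disease involvement, as an eligibility criterion | State of each cavity at the end of surgery; septoplasty is also allowed (2c) |
| Non-parametric ANOVA | 3d | No side-level factor stated | Side and operative findings |

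**Illustrative size of a shift.** The documents give none of these inputs, so all are assumed: correlation ρ = 0.5 between the two sides for end-of-surgery bleeding; correlation r = 0.3 or 0.5 between that bleeding and the later score; and a share p of patients whose easier side is treated.
- Expected bleeding gap between the worse and better side = 2√((1 − ρ)/π) = 2√(0.5/π) = 0.798 SD.
- Shift in the agent-versus-nothing difference = (2p − 1) × 0.798 × r.

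| p | r = 0.3 | r = 0.5 |
|---|---|---|
| 50% (random side) | 0 | 0 |
| 60% | 0.2 × 0.798 × 0.3 = 0.048 SD | 0.2 × 0.798 × 0.5 = 0.080 SD |
| 70% | 0.4 × 0.798 × 0.3 = 0.096 SD | 0.4 × 0.798 × 0.5 = 0.160 SD |

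If instead the bloodier side is treated in 60% or 70%, the sizes are the same with the sign reversed. Against the planned d = 0.5, 0.048/0.5 is about 10% and 0.160/0.5 is 32%.

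**What the shift does to a test.** Simulated with 122 pairs, r = 0.5, two-sided 0.017 (2c does not state sidedness), and both between-side correlations (bleeding and outcome) at 0.5 unless stated:
- No true effect, easier side treated in 60% / 70%: rejection is about 6.4% / 26% with a signed-rank test, but about 0.6% / 5% with the Mann-Whitney test named in 2c.
- Signed-rank at 70%, moving the two correlations separately: about 10% (bleeding 0.8, outcome 0.5) to 47% (bleeding 0.5, outcome 0.7).
- True benefit of 0.5 SD, bloodier side treated in 70% instead of random side: power falls from 99.9% to 90% with signed-rank, and from about 97.5% to about 62% with Mann-Whitney.

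These rates vary too much with the test and the correlations for any one of them to be given as the size of the problem. The assumed shift, about 0.05–0.16 SD, is the usable summary.

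**The case against.** A reader might go further than the documents allow in four ways.

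*That no rule exists.* The text supplied does not include the section 16 attachments, the questionnaires cited in 2c or the consent form listed in section 13. A rule could be there. What stands is that the two sections that ask for it do not give it.

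*That the side was in fact chosen on findings, or that the result is biased.* No section says so. An unstated rule could be harmless, such as a fixed side or alternation unrelated to the state of the cavity. The plan claims only a prospective comparison and never claims randomisation. The point is what the plan permits.

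*That nothing planned could reveal selection.* Section 11c says that pre-treatment imaging is acquired, and 3b item d includes pre-operative and day-0 ratings. If these are available by side, imbalance could point to selection. Their use is limited: 3b does not say that ratings are taken per nostril, and the list of information sources in section 15 leaves radiology results unmarked. Nor does the chart list in 11c ("This includes the sex, ethnicity, age, surgical pathology, treatment type and duration") prove that operative findings go unrecorded. It belongs to an answer on the master list and is not a case report form; the physician questionnaire was not supplied.

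*That false superiority would be around 26%.* That figure needs a signed-rank test, which the plan does not name, and specific assumed correlations. The test named in 2c gives about 5% on the same inputs.

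What remains after these limits is narrower and still matters: no stated step rules out selection of side on operative findings.

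**Conclusion.** The point holds as an unstated allocation rule in the study's main comparison. Followed as written, the plan lets the side be chosen after both cavities are visible, and pairing, eligibility and analysis do not correct for that. The direction of any bias is unknown. Its size is also unknown: 0.05–0.16 SD is an illustration that assumes 60–70% preferential choice, r of 0.3–0.5 and a between-side bleeding correlation of 0.5. It shows that bias is possible, not that it is large or that it happened. The case for acting rests on the missing rule, not on those figures. Confidence is moderate because the attachments and consent form were not available.

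**What to change.** **If accrual is open:** state in 3b that the treated side (left or right) is assigned 1:1 at random, with the assignment concealed and revealed only after both cavities are completed. The cost is an allocation list, sealed envelopes and an amendment. No patients or visits are added: 122 evaluable and 144 enrolled stand.

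**If accrual is closed,** as the marked item 8c of the expedited-review section (only data analysis remaining) indicates: report how the side was chosen and the left/right split, as far as the records allow. If it was not randomised, label the result a non-randomised within-patient comparison and do not present it as a definitive answer on superiority. Any imaging or pre-operative ratings available by side may be tabulated as supporting information, with the caveat that balance would not rule out selection on operative findings. The cost is a look-up in at most 144 records, which may not all hold the needed detail, plus a methods paragraph and careful wording of the conclusion.

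If a rule already exists in an attachment, it is enough to copy it into 3b and confirm that it was followed, provided that it makes the choice of side independent of operative findings.

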**1. Background**

**Protocol Title:** Analysis of hemostatic agents compared to physiologic hemostasis

---

Page numbers from a sponsor's protocol/grant may be referenced in 1a and 1b.

- a) **Provide an introduction and background information. Describe past experimental and/or clinical findings leading to the formulation of the study, if applicable. Investigator Initiated studies must cite references in the response provided or attach a bibliography. *\*?HELP?\****

In this study we wish to determine if the use of hemostatic agents after endoscopic sinus surgery is superior to no agent at all. We will treat patients with one of many different FDA approved hemostatic agents in one of their nostrils and compare it to a side in which no therapy is applied. We will then evaluate qualities of the patient's recovery (synechia formation, granulation, edema, infection, and time spent debriding the sinuses) in response to intervention.

Functional endoscopic sinus surgery (ESS) is a safe, commonly performed procedure primarily in an outpatient setting. One of the most prevalent complications is post-operative epistaxis. To prevent this nasal packing is often employed. Traditionally non-absorbable packing was employed; yet, this has fallen out of favor with most otolaryngologists considering the great discomfort of the packing, especially upon removal (von Schoenberg). In addition to this, with removal of non-absorbable packing interruption of the wound bed is inevitable. This has led to a paradigm shift towards absorbable packing, which are biomaterials that provide substrate to stimulate clotting. Absorbable hemostatic agents tend to spare the mucosa and are less painful upon removal (Maccabee). However, absorbable packing comes with the possible drawback of increased rates of synechia formation secondary to initiation of local inflammation (Valentine). Standard of care is no packing, one of these types of absorbable packing, or removing packing.

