## 2. Purpose of the study

- a) Provide a brief lay summary of the project in <200 words. The lay summary should be readily understandable to the general public.

Our study is a prospective comparison between absorbable hemostatic agents as a group and the body's natural hemostatic ability without aid of therapy in patients undergoing bilateral sinus surgery with or without septoplasty.

Page numbers from a sponsor's protocol/grant may be referenced in 2b and 2c.

- b) List your research objectives (specific aims & hypotheses of the study).

The purpose of this study is to evaluate the efficacy of absorbable hemostatic agents in comparison with physiologic hemostasis after endoscopic sinus surgery. We aim to determine the relative efficacy of hemostatic agents to halt epistaxis and compare this with the degree of epistaxis observed without therapy. Also will evaluate objective healing parameters.

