- 3) Obstruction/Blockage of sinus passage. Post operative irrigations will remove any excess material. Also, debridement during post operative visits will remove any material that irrigation can't.
- 4) Pain
- 5) Infection-- [name] and [name] will evaluate patients for signs of infection during post operative visits.
- 6) Delayed/ Asymmetric healing. One nostril will receive therapy while the other will not receive therapy. If therapy decreases wound healing time, asymmetric healing/healing may occur.
- 7) Embolization and Death. This risk has been identified with Arista AH. However, this risk exists only if Arista AH is directly injected into blood vessels. In this study we will only apply Arista topically to the interior of a patient's nostril. Nothing will be injected into or applied to an open vessel. Furthermore, any excess Arista will be removed with postoperative irrigation.

There are no other additional adverse reactions to these products associated with being in this study.

5. **Describe any risks related to performing study procedures. Please include all investigational, non-investigational, and non-invasive procedures (e.g., surgery, blood draws, treadmill tests).**

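### Debriding time includes removal of the study product on the treated side only, so a longer or equal treated-side time cannot be read as worse or equal healing

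*Combined protocol and SAP*

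**What the plan says.** Section 1a says the trial will evaluate "qualities of the patient's recovery (synechia formation, granulation, edema, infection, and time spent debriding the sinuses) in response to intervention". Section 2b adds to the aims: "Also will evaluate objective healing parameters". Under section 2c, physicians "will rate objective measures such as mucosal edema, infection, time spent debriding, and synechiae formation". The same section goes on: "Surgical healing outcomes will be noted during routine postoperative visits 1 and 2 weeks after surgery".

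Section 3b(b) puts an agent in one nostril and nothing in the other. Section 3b(c) lets the product stay until it is absorbed or taken out at a visit, says that irrigation clears much of it, and then states: "Any residual material is removed in the office on normal, (Standard of Care) post-operative debridement on weeks 1, 2, and/or 6". Section 9.4, under obstruction, repeats that "debridement during post operative visits will remove any material that irrigation can't".

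Section 3b(f) has the physician record time spent debriding, with no mention of separating product removal from other debridement. Section 3d plans descriptive statistics and a non-parametric ANOVA of the physician data, with no adjustment for product removal.

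**The concern.** The timed procedure includes taking out the intervention, and only one side has it. Time spent clearing product is zero by design in the untreated nostril and zero or more in the treated one. Using each patient as their own control does not cancel this, because the asymmetry is the treatment contrast itself.

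Consider a patient who heals identically on both sides but has undissolved product at week 1. That patient can show a longer time on the treated side. If the result is reported as recovery, it looks like harm from the agent. Conversely, a real reduction in crusting could be offset by clearing time and reported as no difference.

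Pooling adds to this. The agents are compared as one group, yet section 1a describes Arista and Nexfoam as cleared rapidly and Nasopore as a dressing meant to hold mucosal surfaces apart. The pooled difference may therefore vary with the mix of products used.

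**Working it through.** **1. Does removal fall inside the recorded time?** Removal takes place at debridement in weeks 1, 2 and/or 6 (3b(c)). Debriding time is recorded at weeks 1, 3 and 6 (3b(f)), while section 2c places the healing outcomes at weeks 1 and 2. These schedules must be reconciled. Within section 3b, removal and recording coincide at weeks 1 and 6.

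**2. Direction.** Write the treated-side time as H_T + R and the untreated-side time as H_C. H is time spent on crust, clot or adhesions, and R ≥ 0 is time spent clearing product. The observed difference is (H_T − H_C) + R.

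- Observed difference above or equal to zero: H_T − H_C can have either sign, so healing is not identified.
- Observed difference below zero: H_T − H_C is at least as far below zero, so the result is conservative for benefit.

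**3. The plan's own sample size (context only).** Section 2c gives 122 per group for d = 0.5 and power 0.80. A two-group Wilcoxon-Mann-Whitney calculation (noncentral t, relative efficiency 3/π) gives exactly 122 at a one-sided alpha of 0.05/30 = 0.00167. The printed alpha of 0.017 gives 75 one-sided or 89 two-sided. For dropout, 122/0.85 = 143.5, so 144. The alpha discrepancy is a separate matter, and both values are carried below.

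**4. Illustration of size.** The documents give neither a clearing time nor an SD, so every input except n and alpha is assumed.

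- Shift: an average of 1 minute of clearing over a single-side SD of 3 to 4 minutes gives 1/4 = 0.25 SD to 1/3 = 0.33 SD.
- SD of the paired difference = SD × √(2(1 − ρ)). At an assumed ρ = 0.5 this equals the single-side SD, so the standardised shift b is 0.25 to 0.33.
- n = 122 pairs, √122 = 11.045. Two-sided critical values are 2.387 (alpha 0.017) and 3.144 (alpha 0.00167).
- With no healing difference, P(significant) = Φ(b√n − z) + Φ(−b√n − z), a paired normal approximation.

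For b = 0.25, b√n = 2.761: Φ(2.761 − 2.387) ≈ 0.65 and Φ(2.761 − 3.144) ≈ 0.35. For b = 0.33, b√n = 3.645: Φ(1.258) ≈ 0.90 and Φ(0.501) ≈ 0.69. The second term is negligible in both cases.

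| b (SD of side difference) | alpha 0.017 | alpha 0.00167 |
|---|---|---|
| 0.1 | 10% | 2% |
| 0.2 | 43% | 17% |
| 0.25 | 65% | 35% |
| 0.3 | 82% | 57% |
| 0.33 | 90% | 69% |
| 0.5 | 99.9% | 99% |

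An 80% chance of a spurious difference needs b = 0.29 at alpha 0.017 or b = 0.36 at 0.00167. If only half the patients had residual product, a shift of 0.33 would average 0.165 (SD held fixed), giving about 29% and 9%.

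**The case against.** **The amount of residual product may be small.** Irrigation is said to clear much of it, two agents are described as cleared rapidly, and Nasopore is described as able to fragment. This stands. A reader might infer that the endpoint is driven by the presence of the pack. The documents do not support that, because they give no clearing times and no amounts of residual product.

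**The bias has one direction.** A reader might also infer that debriding time says nothing about healing whatever the result. That goes too far, since removal cannot explain a shorter treated-side time.

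**The physician form is an attachment that is not shown.** It may already time each nostril, split the time or note residual product. Section 2c speaks of physicians rating this item alongside 1–10 patient ratings, so it may be a score rather than minutes. This stands as a limit on certainty. If the form does split the time, sections 3b(f) and 3d should say so.

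**Total time is a legitimate outcome.** Clearing product is a real consequence of using an agent, and section 2c does not say outright that debriding time is one of its surgical healing outcomes. This supports keeping total time as a measure of burden. It does not support section 1a's listing of it as a quality of recovery.

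**The numbers rest on chosen inputs.** This also stands. Testing at 0.05 with a 0.33 SD shift would give about 95%, but the plan does not use 0.05 per test, so that figure should not be quoted as the trial's risk.

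**Conclusion.** The concern holds in a limited form. As the visible text stands, the side-to-side difference in debriding time mixes healing with product removal, on the treated side only and to an unknown degree. A longer treated-side time does not show worse healing, and a null result does not show equal healing. A shorter treated-side time would be conservative evidence of benefit.

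A modest clearing time could matter: roughly 65–90% spurious significance at alpha 0.017 and 35–69% at 0.00167. Those figures depend on an assumed shift of 0.25–0.33 SD, ρ = 0.5, 122 pairs and a normal approximation. They fall sharply if residual product is uncommon.

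The reach is one of five listed physician measures, in a plan that names no primary outcome. The mechanism does not alter the recording of synechiae, granulation, edema or infection.

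**What to change.** In sections 3b(f) and 3d, define total debriding time per nostril as a measure of procedure burden, not a healing outcome, and report it by product and visit.

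**If data are still being collected** and the physician form does not already do so, add for each side at each visit a tick for residual product and a separate time for clearing it. Use the remaining debridement time as the healing measure.

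**If only analysis remains**, as the ticked item 8(c) under Expedited Paragraphs indicates, relabel the outcome, restrict the interpretation to the one-directional reading above, and use any residual product already recorded.

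The cost is one time field and one tick box per side, or a wording change alone. The downside is that the split is approximate when crust and product are mixed, and it is made by an assessor who can see the product.
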